## 8 STUDY TREATMENTS

### 8.1 Method of Assigning Participants to Treatment Groups

Participants will be computer sequence-randomized to receive either oral daily dosing of 1200 mg ALA or placebo.

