Rationale for Number of Participants	The target enrollment for this study is 50 participants, based on a conservative approach to determine the sample size needed to evaluate the effect of ALA supplementation. Two recent studies evaluating the medical management of cystinuric individuals have reported that among individuals who are compliant in taking medications, the average number of stone events per person is approximately 1 per year (Reference #'s 5, 9). The current study design will be powered at 90% to detect a clinically meaningful reduction of stone events at 50% (0.5 stone events per year) with two-tailed $\alpha = 0.05$ . Based on a two-sided t-test, the following scenarios were considered for the standard deviation (SD) for the sample and sample size (n): SD 0.5, n=11; SD 0.75, n=24; SD 1, n=42. To account for a small dropout rate over the study duration, the enrollment goal of 50 participants was proposed.

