Clinical data including medical history, plain KUB x-ray and renal ultrasound, routine blood work, and 24-hour urine collections for all participants will be collected as part of normal clinical care at routine clinical visit intervals, which currently occur every 4 months. Routine clinical care for participants will not be altered in any way outside of administration of the supplement or placebo. Routine clinical care generally consists of office visits every 4 months at which time, as medically necessary as determined by the study investigator, an imaging study is performed (plain KUB x-ray, ultrasound, or CT scan if clinically indicated), a 24-hour urine collection is done to check quantitative urinary cystine levels, and blood is drawn to evaluate electrolyte levels as well as renal function. During routine visits for blood and urine tests, any discarded blood and urine specimens will be collected for research testing. No additional blood draw or urine collection will be performed for this study. From discarded routine specimens provided during these clinic visits, metallomic and metabolomics profiling will be performed for all participants using discarded samples material. This is comprised of mass spectrometry and elemental analysis of samples performed in our research lab. Quality of life measurement, as recorded by the Wisconsin Stone-quality of life questionnaire (Wisconsin Stone-QoL), will also be evaluated.

Recurrent stone events, defined by symptomatic or silent stone recurrence, is the primary endpoint in this study. It will be documented in this study cohort, and compared between treatment and placebo groups to determine treatment effect. If stones are removed for surgery or spontaneously passed by participants, any discarded stone specimens not needed for clinical care will also be subjected to metabolomic and metallomic analysis.

At the end of the three years of study drug treatment, all participants will undergo a low dose non-contrast CT scan to look for a silent change in stone size. As this is a pilot study, recruitment will be limited to target enrollment of 50 participants (25 for each treatment arm). Treatment will continue for a total of 3 years and after treatment completion, participants will be followed for an additional 2 years to evaluate for change in clinical status or adverse events resultant from ALA administration.

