### 8.2 Blinding

Both participants and study team members will be blinded to treatment arm. The following study procedures will be in place to ensure double-blind administration of study treatments:

- Randomization will occur at time of first screening visit and results will be

provided to the UCSF Pharmacy compounding services

- Randomization will be controlled by the UCSF Pharmacy compounding service who will provide treatment packages to the study coordinator who will provide them to the study participant. Treatment packages will contain insert materials but no markings that will allow participants to know which study arm they have been randomized to.
- Access to randomized code will be strictly controlled; study investigators and clinical coordinators will not have access to the randomized code unless a need for un-blinding arises.
- Packaging and labeling of test and control treatments will be identical.

The study blind will be broken on completion of the clinical study and after the study database has been locked. In the event of an adverse event, the study investigator may decide to un-blind himself to determine if ALA is the cause. In addition, when 50% of target participants have been enrolled and on the study protocol for 6 months, an interim analysis will be performed by an un-blinded statistician to evaluate for ALA clinical effects. At that point, if it is found that clinical outcomes for ALA-treated participants are significantly improved compared to the placebo arm, study investigators may elect to complete the trial early and provide all participants with ALA.

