### 10.1 Visit 1 (Initial Visit)

1. Review the study with the participant (participant's legal representative) and obtain written informed consent and HIPAA authorization.
2. Assign the participant a unique study ID number.

3. Record demographics data.
4. Record medical history, including a history of stone disease and family history of stone disease, date of first diagnosis, and prior surgical interventions.
5. Record concomitant medications.
6. Perform a complete physical examination and record vital signs if possible
7. Administer the Wisconsin Stone-QoL survey.
8. Collect routine blood for clinical laboratory tests (CBCs, chemistries, BUN, creatinine) if medically necessary as determined by the study investigator
9. Perform routine 24hr urine testing.
10. Collect passed stone specimens, if presented.
11. Collect discarded blood and urine specimens for research purposes if presented.

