### 15.3 Sample Size and Randomization

The target enrollment for this study is 50 participants, based on a conservative approach to determine the sample size needed to evaluate the effect of ALA supplementation. Two recent studies evaluating the medical management of cystinuric individuals have reported that among individuals who are compliant in taking medications, the average number of stone events per person is approximately 1 per year (Reference #'s 5, 9). The current study design will be powered at 90% to detect a clinically meaningful reduction of stone events at 50% (0.5 stone events per year) with two-tailed  $\alpha = 0.05$ . Based on a two-sided t- test, the following scenarios were considered for the standard deviation (SD) for the sample and sample size (n): SD 0.5, n=11; SD 0.75, n=24; SD 1, n=42. To account for a small dropout rate over the study duration, the enrollment of 50 participants was proposed. At UCSF, clinical volume approximates 60 nephrolithiasis patients per week, including those with cystinuria. At a recent cystinuria outreach event led by [name] at UCSF (<http://[name].ucsf.edu/?q=news/june-18-2015-cystine-patient-symposium>), over 50 individuals with cystinuria attended among over 100 participants overall. We anticipate that 6-8 months will be required to accrue these participants.

Participants will be computer sequence-randomized to receive either ALA or placebo.

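### The stated primary test leaves out prior stone rate, which costs precision in a 50-person trial, and the allocation scheme is not specified

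*Combined protocol and SAP*

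**What the plan says.** **Allocation.** Section 8.1 reads: "Participants will be computer sequence-randomized to receive either oral daily dosing of 1200 mg ALA or placebo". Section 15.3, whose title covers randomization, adds only "Participants will be computer sequence-randomized to receive either ALA or placebo". Section 4.1 says "recruitment will be limited to target enrollment of 50 participants (25 for each treatment arm"). Section 8.2 adds that "Randomization will be controlled by the UCSF Pharmacy compounding service", that access to the code is restricted, and that allocation takes place at the first screening visit. No section says how the list is generated, and none names blocks, strata or minimisation.

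**Analysis.** The statistics part of the synopsis compares symptomatic and silent recurrence rates between arms by a two-sided t-test. Section 15.2 repeats the endpoint and the intention-to-treat principle but names no model or covariate. Section 15 promises a detailed SAP before the final data are analysed.

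**Baseline stone activity.** Section 6.2 requires previous cystine stones but sets no minimum or maximum frequency and no time limit. Section 10.1 has staff "Record medical history, including a history of stone disease and family history of stone disease", together with date of first diagnosis and prior surgical interventions. It asks for no event count and sets no look-back period. It also does not place this item before or after allocation.

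**The concern.** The primary endpoint is recurrent stone events over three years. People who form stones often before entry will probably continue to do so, although the documents give no data on this. The plan itself allows for wide variation: its SD scenarios run up to 1 against a control mean of about 1 event per year. With 50 participants, that spread between people makes up much of the standard error of the arm difference. A baseline measure that explains part of it would narrow the confidence interval at almost no cost. The plan takes a stone history and uses it in neither allocation nor analysis.

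At stake is whether a three-year trial in a rare disease can detect the 50% reduction it targets, and whether a reader would accept the result if one arm happened to contain more frequent formers.

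**Working it through.** **1. The plan's own sample size.** Section 15.3 takes as its control rate that "the average number of stone events per person is approximately 1 per year", a difference of 0.5 events/year, 90% power and two-sided alpha 0.05. It gives n = 11, 24 and 42 for SD 0.5, 0.75 and 1.
- One-sample form, (SD × (1.960 + 1.282)/0.5)²: 10.5, 23.6 and 42.0. This matches the stated figures.
- Two-arm form, twice that per arm: 22, 48 and 85 per arm. This does not match.

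That discrepancy is a separate matter. It is relevant here because power at 25 per arm is about 94%, 65% and 42% (normal approximation), so precision is scarce unless the SD is near 0.5.

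**2. Unequal arm sizes, if allocation is simple.**
- P(exactly 25:25) = C(50,25)/2⁵⁰ = 0.112, about 1 in 9.
- P(30:20 or worse) = 0.203.

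| SD | Power at 25:25 | Power at 30:20 |
|---|---|---|
| 0.5 | 94.2% | 93.4% |
| 0.75 | 65.4% | 63.7% |
| 1 | 42.4% | 41.0% |

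The loss is under 2 points in every row.

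**3. Imbalance in frequent formers.** The documents give neither the share nor the rate of frequent formers, so both are assumed.
- Exact enumeration under simple allocation, with 15, 20 or 25 frequent formers among 50: the arms differ by 20 points or more with probability 0.136, 0.155 and 0.203. With 10 frequent formers it is 0.081.
- With a forced 25:25 split and no strata, the same probability is 7% to 26% over 10 to 25 frequent formers. Blocking alone therefore does not address this.
- Effect of a 20-point gap at 1.6 against 0.4 events/year: 0.20 × 1.2 = 0.24 events/year. Other assumed rates (1.5 to 3 against 0.5 to 0.75) give 0.15 to 0.5.

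**4. That shift against the standard error.** Take three-year Poisson counts within each group and a share p of frequent formers.
- Control mean: 0.3 × 1.6 + 0.7 × 0.4 = 0.76 at p = 0.3, and 1.0 at p = 0.5.
- Variance of a person's annual rate: p(1 − p) × 1.2² + mean/3. This is 0.302 + 0.253 = 0.556 (SD 0.75) at p = 0.3, and 0.360 + 0.333 = 0.693 (SD 0.83) at p = 0.5. Both SDs lie within the plan's range.
- SE at 25 per arm: SD × √(2/25) = 0.21 to 0.24.

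A shift of 0.24 is therefore about one standard error. The between-group part is 0.302/0.556 = 54% and 0.360/0.693 = 52% of the variance, and that is what a baseline covariate can remove.

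**5. Simulated power for a 50% reduction.** Settings: 50 participants, 30-50% frequent formers, 1.6 against 0.4 events/year, no dropout, and a two-level baseline stratum as the covariate.

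| Allocation and analysis | Power | Type I error |
|---|---|---|
| Simple, unadjusted t-test | about 55-72% | about 5% |
| Simple, adjusted for stratum | about 82-92% | about 5% |
| Simple, adjusted, 25% of participants misclassified | about 62-76% | about 5% |
| Stratified, unadjusted t-test | about 59-78% | about 0.5% |

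Stratified allocation with adjustment adds only about 2-3 points over adjustment alone, and only when the strata are accurate.

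**The case against.** **The documents do not say that allocation is simple.** A reader might infer from 8.1 and 15.3 that there are no blocks and that 25 per arm would be met only one time in nine. The text does not support that. A computer-generated sequence can be blocked or fixed at 25:25, and a stated 25 per arm under pharmacy control fits a restricted list at least as well. The 11% is conditional, and missing 25:25 matters little in any case. This objection stands in full. What remains is missing detail.

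**Chance imbalance is not bias.** A reader might also infer that an uneven share of frequent formers would invalidate the comparison. It would not. The unadjusted test under simple allocation keeps its type I error near 5%, because its standard error already includes this variation. This stands too, and it makes the point one of precision.

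**The sizes rest on assumed rates.** Correct. The documents give no share, no rate gap and no data on how well past frequency predicts future events. The direction of the gain is not in doubt if baseline rate is prognostic, but its size is.

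**The promised SAP could add the covariate.** It could, but the current text does not commit to it. The SAP is due only before the final analysis, and an interim comparison by an unblinded statistician may come first. A usable baseline count also has to be defined at entry, and Visit 1 does not yet define one.

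**Conclusion.** The concern holds as a point about precision. The stated primary analysis omits baseline stone rate, which is the obvious candidate predictor of the endpoint. Under the assumed rates, adjustment raises power by roughly 20 points or more. With 25% of participants misclassified, adjusted power is only about 62-76%, so most of that gain is lost. The simulation also assumes Poisson counts within groups and no dropout, and it tests a 50% reduction. That is 0.38 events/year at a 30% share (half of 0.76) and reaches the plan's 0.5 only at a 50% share (half of 1.0).

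The under-specified allocation is a lesser, reporting matter. It should be stated, but the documents do not show it to be defective, and stratifying it is a refinement of the covariate and not a substitute for it.

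**What to change.** 1. **Visit 1 form (10.1).** Before allocation, record the number of stone events over a fixed look-back period. State the length of that period and whether silent events count.
2. **Primary analysis (synopsis, 15.2 and the SAP).** Replace the unadjusted t-test with a linear model for events per year, containing treatment arm and baseline stone rate. Fix this before any unblinded look, and use the same covariate at the interim.
3. **Allocation (8.1 and 15.3).** State 1:1 allocation by permuted blocks of varying size, with the list held by the pharmacy, preferably stratified on the same baseline rate. If it is stratified, the stratum must be in the model, because the unadjusted t-test would then be conservative (type I error about 0.5% under the assumptions above).

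**Cost.** One defined history item, which Visit 1 does not at present collect in this form, and one degree of freedom. If stratified, the pharmacy holds a two-stratum list in place of one sequence. No extra visits or participants are needed. The gain depends on how accurate the recalled or abstracted history is.

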### 8.2 Blinding

Both participants and study team members will be blinded to treatment arm. The following study procedures will be in place to ensure double-blind administration of study treatments:

- Randomization will occur at time of first screening visit and results will be

provided to the UCSF Pharmacy compounding services

- Randomization will be controlled by the UCSF Pharmacy compounding service who will provide treatment packages to the study coordinator who will provide them to the study participant. Treatment packages will contain insert materials but no markings that will allow participants to know which study arm they have been randomized to.
- Access to randomized code will be strictly controlled; study investigators and clinical coordinators will not have access to the randomized code unless a need for un-blinding arises.
- Packaging and labeling of test and control treatments will be identical.

The study blind will be broken on completion of the clinical study and after the study database has been locked. In the event of an adverse event, the study investigator may decide to un-blind himself to determine if ALA is the cause. In addition, when 50% of target participants have been enrolled and on the study protocol for 6 months, an interim analysis will be performed by an un-blinded statistician to evaluate for ALA clinical effects. At that point, if it is found that clinical outcomes for ALA-treated participants are significantly improved compared to the placebo arm, study investigators may elect to complete the trial early and provide all participants with ALA.

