	pregnancy during the study duration; unable to give informed consent; non-English primary language; pregnancy, lactation, or child- bearing age without birth control devices; and serious illness likely to cause death within the next 5 years.
TEST PRODUCT, DOSE, AND ROUTE OF ADMINISTRATION	The test product is 600 mg of ALA administered orally twice a day for three years.
CONTROL PRODUCT, DOSE AND ROUTE OF ADMINISTRATION	The control product is a sucrose tablet containing 10 mg of sucrose, given orally twice a day for three years.
DURATION OF PARTICIPATION AND DURATION OF STUDY	Screening: 1 week to determine eligibility Treatment: 3 years with visits every 4 months Follow-up: 2 years with visits every 4 months

CONCOMITANT MEDICATIONS	
Allowed: The participants will be allowed to continue any medications they are currently taking.
 
Prohibited: No medications will be strictly prohibited. However, alpha-mercaptobutyrylthiolglycine and D-penicillamine, two medications currently used to treat cystinuria, are both thought to bind the sulfhydryl groups of cysteine preventing the molecules from binding together and resulting in the insoluble cystine molecule. Both medications are not used with great frequency and both are not very effective. As they may interfere with the mechanism of action of ALA, participants of this study who take alpha-mercaptobutyrylthiolglycine and/or D-penicillamine will be asked to stop these medications 12 weeks prior to starting the treatment portion of the study as a washout period to ensure no harmful effects result from stopping these therapies. If they chose not to stop, at the discretion of the Principal Investigator, the participant will be allowed to participate and the study will simply document the use of Thiola throughout the course of the study and may look at these participants separately in the final analysis.

EFFICACY EVALUATIONS	Efficacy evaluations will include determination of stone recurrences on clinical history, exam, and radiographic review; quantitative 24-hour urinary cystine; and urinary, blood, and stone metallomic and metabolomic profiling.

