### 4 STUDY DESIGN

#### 4.1 Study Overview

This study will be a single center, randomized double-blind placebo-controlled trial designed to assess the effect of daily 1200 mg ALA supplementation for three years on kidney stone recurrence in participants with cystinuria. Participants will be computer sequence-randomized to receive either oral daily dosing of 1200 mg ALA or placebo. Participants will be allowed to continue potassium citrate treatment, the currently mainstay of cystinuria treatment, so as to avoid inducing worsened clinical events. If participants are taking D-penicillamine and alpha-mercaptopropionylglycine at the time of study enrollment, they will be asked to stop these medications 12 weeks prior to starting the treatment portion of the study as a washout period to ensure no harmful effects result

from stopping these therapies. If they chose not to stop, at the discretion of the Principal Investigator, the participant will be allowed to participate and the study will simply document the use of Thiola throughout the course of the study. A minority of cystinuric stone formers take D-penicillamine and alpha- mercaptopropionylglycine and our clinical experience reflects that these medications do not demonstrate a high efficacy for stone prevention. We therefore do not think that stopping these drugs will worsen clinical stone outcomes, but to ensure this is the case, participants who are on these medications and choose to stop, will be observed for a 12-week washout period after stopping D-penicillamine and alpha-mercaptopropionylglycine and prior to starting ALA. We anticipate participant enrollment to last 6-8 months. The secondary objectives of this study are to determine the effect of ALA on quantitative urinary cystine, cystine solubility, and metallomic and metabolomics profiles in participants with cystinuria to help determine the mechanism(s) of action of ALA in cystinuric individuals. Both study participants and study team members will be blinded to the treatment.

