### 7.1 Allowed Medications and Treatments

No medications will be strictly prohibited. However, alpha-mercaptopyrionylglycine and D-penicillamine, two medications currently used to treat cystinuria, are both thought to bind the sulfhydryl groups of cysteine preventing the molecules from binding together resulting in the insoluble cystine molecule. Both medications are not used with great frequency and both are not very effective. As they may interfere with the mechanism of action of ALA, participants of this study who take alpha-mercaptopyrionylglycine and/or D-penicillamine will be asked to stop these medications 12 weeks prior to starting the treatment portion of the study as a washout period to ensure no harmful effects result from stopping these therapies. If they choose not to, at the discretion of the Principal Investigator, the participant will be allowed to participate and the study will simply document the use of Thiola throughout the course of the study and may look at these participants separately in the final analysis. .

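### Randomisation is set at the first screening visit, before eligibility and any 12-week thiol washout are complete, and month 0 is not defined

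*Combined protocol and SAP*

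**What the plan says.** **Timing of allocation.** Section 8.2: "Randomization will occur at time of first screening visit". The duration entry of the synopsis gives screening as "1 week to determine eligibility".

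**Washout.** Section 7.1 says that users of the two thiol drugs "will be asked to stop these medications 12 weeks prior to starting the treatment portion of the study as a washout period". Section 4.1 identifies them at enrolment and adds that they "will be observed for a 12-week washout period after stopping D-penicillamine" and the other thiol. Stopping is voluntary. For those who decline, if the investigator agrees, "the participant will be allowed to participate and the study will simply document the use of Thiola throughout the course of the study", and the analysis "may look at these participants separately in the final analysis".

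**Visits.** Section 9 requires consent before any study-related activity, and section 10.1 takes it at Visit 1, which section 9.1.1 treats as the combined baseline and screening visit. The 24-hour urine and the QoL survey are done at that visit. Neither section 10 nor Appendix 1 lists an eligibility confirmation, a randomisation or first-dispensing step, a washout contact or a second pre-treatment baseline.

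**Analysis.** All enrolled participants are analysed (15.1), by intention to treat (15.2), and withdrawals are not replaced (12.4). The primary endpoint covers a 3-year treatment period with no stated start date. The interim takes place once half the target has been on the protocol for 6 months (8.2).

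**The concern.** Allocation should come as late as is practical, so that people who will never start treatment are not carried in the randomised comparison. Here a participant can be allocated, then found ineligible or lost during 12 weeks off a thiol, and still count in the analysis without having taken study drug. With 50 participants and no replacement, each such loss matters.

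Two further matters follow. If no day is named as month 0, washout weeks may or may not count towards the visits, the 3-year window and the interim, and that interim can lead to early completion. The only scheduled pre-treatment 24-hour urine is also taken while washout participants are still on a thiol. Section 1 describes thiols as lowering urinary cystine, so that sample is a poor baseline for a named secondary outcome.

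**Working it through.** **Order of events**

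1. Randomisation is at the first screening visit (8.2).
2. Eligibility may take a further week (synopsis).
3. The washout is requested by the study, so it needs consent first (section 9), and consent is taken at Visit 1 (10.1).
4. The washout therefore follows Visit 1, and so follows allocation. This is an inference from three places; no sentence states it.

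**Untreated time, only if the clock runs from Visit 1**

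- 36-month window: 12/156 weeks = 7.7%.
- 6-month interim: 12/26 weeks = 46%.

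**The plan's own sample sizes (15.3)**

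The plan gives n = 11, 24 and 42 for SD 0.5, 0.75 and 1, with a difference of 0.5 events per year, 90% power and two-sided alpha 0.05. The one-sample formula (SD × (1.960 + 1.282)/0.5)² gives 10.5, 23.6 and 42.03, which matches. A two-sample comparison needs 22, 48 and 85 per arm. That is a separate and larger problem. It matters here only because the starting power is not 90%.

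**Power with 25 per arm (4.1)**

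Power = Φ(δ/(SD × √(2/25)) − 1.960). The share f who wash out is an assumption, because section 4.1 says only that a minority take these drugs. Untreated time reduces the effect to δ = 0.5 × (1 − f × 12/156).

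| SD | No washout time counted | f = 10% (δ 0.496) | f = 25% (δ 0.490) | f = 50% (δ 0.481) |
|---|---|---|---|---|
| 0.5 | 94.2% | 93.9% | 93.4% | 92.5% |
| 0.75 | 65.4% | 64.8% | 63.7% | 62.0% |
| 1 | 42.4% | 41.8% | 41.1% | 39.7% |

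The cost runs from 0.3 points (SD 0.5, f = 10%) to 3.4 points (SD 0.75, f = 50%).

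**Adding losses in washout**

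Assume that 20% of washout participants are lost with no outcome data. At f = 50% that is 5 of 50 people, leaving 25 × (1 − 0.5 × 0.2) = 22.5 per arm. Power at SD 0.75 falls to 57.5%, a drop of 7.9 points from 65.4%. At f = 10% and 25% it is 63.9% and 61.5%. These comparisons assume that, after the change, recruitment continues until 50 have been randomised.

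If those five people are instead followed off drug and counted, the effect is 0.5 × (1 − 0.10 − 0.40 × 12/156) = 0.435. Power is then Φ(0.435/0.212 − 1.960), about 53.5%, a drop of about 12 points.

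**Interim**

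The average effect at 6 months is 0.5 × (1 − f × 12/26) = 0.477, 0.442 and 0.385 for f = 10%, 25% and 50%.

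**Chance imbalance of thiol users**

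No stratification is described. With an assumed 10 users, each allocated 1:1 at random, a split of 7:3 or worse has probability 34%. With an assumed 15, 10:5 or worse has probability 30%. Both counts are illustrative.

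**The case against.** A reader might infer that washout participants receive only about 33 months of drug by month 36 (36 months less 12 weeks is 33.2). The documents do not support that as a fact. Sections 4.1 and 9.1.6 place the CT scan at Visit 10 after three years of study drug, section 10 has participants stop after a 36-month treatment period, and the washout precedes the treatment portion. On those words the washout lies outside the endpoint window. What stands is that no start date is given and the visit tables have no first-dose day.

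A reader might also infer that early allocation favours one arm, or that thiol withdrawal confounds the urinary-cystine comparison. Neither follows. Allocation is concealed and blinded, and stopping a thiol affects both arms equally in expectation. It adds noise. No passage defines a change from baseline or names the Visit 1 urine as the analysis baseline.

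Three further points are fair:

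- The eligibility criteria rest mostly on history and records, and section 10.1 orders no test whose result decides entry, so late ineligibility may be rare. The documents allow no estimate.
- Losses before first dose under an intact blind should not differ by arm, so leaving them out by a prespecified rule could be defended. The plan has no such rule and says that everyone enrolled is analysed.
- The protocol considers thiols not very effective, so imbalance in their use may matter little for stone events.

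**Conclusion.** The point holds as an inconsistency that is cheap to remove. Section 8.2 must be reconciled with the screening period and the washout. As written, allocation appears to come first, so people who never start treatment remain in an intention-to-treat set without replacement.

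The size is modest. Untreated time alone costs 0.3 to 3.4 power points over an assumed 10-50% washout share, and only if time runs from Visit 1. Losing 20% of a 50% share as well brings the cost to about 8 points at SD 0.75, or about 12 if those people are followed and counted untreated. The 50% share is an upper assumption, since the documents speak of a minority. The interim is more exposed, at 46% untreated time per washout participant on the same reading.

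Confidence is moderate, because the order of events is inferred. The later SAP foreseen in section 15 can define month 0 and the covariate, but it cannot move an allocation already made or recover a missed baseline.

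**What to change.** In sections 8.2 and 10.1 and Appendix 1:

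- Randomise at first dispensing, once eligibility is confirmed and any washout is complete.
- Define that day as month 0 for visits, the 3-year endpoint window and the interim's 6 months.
- Use as baseline the last routine 24-hour urine and QoL survey completed before first dose.
- For washout participants, either allow one pre-dose collection and dispensing contact, or use the nearest routine collection after washout. The first option means amending the statements in sections 4.1 and 10 that rule out extra urine collections and extra visits. The second adds no burden. But on a four-monthly schedule the next routine collection falls about 5.3 weeks after a washout begun at Visit 1 ends (52/3 − 12), so it is a baseline only if dosing has not yet started.
- In section 15.2, prespecify continuing thiol use at randomisation as a covariate, with all participants retained, in place of the optional separate look. Stratifying on it is optional and would need two pharmacy lists instead of one.

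The cost is a protocol amendment and, for washout participants only, one extra contact, possibly one extra urine collection, and later allocation. The washout and opt-out rules themselves are unchanged.
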